### Concomitant Medication

Partial concomitant medication start and end dates will be used to derive the reference variables for concomitant medication start and end relative to treatment; any imputed dates will be included in the analysis dataset with an identifier as imputed. The reference variables will be used to differentiate before, during, and after treatment for the concomitant medication. The imputed dates will not be used to calculate study day or duration.

Date	Missing Element	Rule
Start Date	day, month, and year	
 
If the medication start date is completely missing and the end date is either after the first dose date or completely missing, then set the missing start date as the first dose date.
 

	day, month only	
 
If the medication start year is same as the year of study start, set to the first dose date; otherwise,
 
Set to January 1st of the year the concomitant medication started
 

	day only	
 
If the medication start year and month are the same as the first dose date, impute the missing day as the first dose date; otherwise,
 
Set start date to the 1st of the month the concomitant medication started.
 

End Date	day, month, and year	
 
If the end date is completely missing or Ongoing is checked, set the missing end date as the last contact date.
 

	day, month only	
 
If the partial end date contains year only, set end date to the earliest of December 31st or the last contact date.
 

	day only	
 
If the partial end date contains month and year, set the end date to the earliest of the last day of the end month reported or the last contact date.
 

Idera Pharmaceuticals, Inc.  
Statistical Analysis Plan  
Protocol Number: 2125-MEL-301

---

## **8.2 DERIVED VARIABLES**

The following sections provide a general description of the derived and transformed variables to be used in data analyses. Separate analysis dataset specifications provide full details on all data derivations and transformations.

### **8.2.1 Reference Dates**

There are three reference dates:

- Because age is an eligibility requirement, the reference date for age is the date initial informed consent for study participation was signed.
- The safety reference date is the first treatment start date and will be used to calculate study day for safety measures.
- The efficacy reference date is the date of randomization.

### **8.2.2 Study Day for Safety**

If the date of interest occurs on or after the safety reference date, then the safety study day will be calculated as (date of interest - safety reference date) + 1. If the date of interest occurs before the safety reference date, then the safety study day will be calculated as (date of interest – safety reference date). There is no safety study day 0.

### **8.2.3 Study Day for Efficacy**

If the date of interest occurs on or after the efficacy reference date, then the efficacy study day will be calculated as (date of interest - efficacy reference date) + 1. If the date of interest occurs prior to the efficacy reference date, then efficacy study day will be calculated as (date of interest – efficacy reference date). There is no efficacy study day 0. Subjects randomized and not treated will be censored at study day 1.

### **8.2.4 Durations**

When durations which are initially calculated in days are to be reported in months, divide the number of days by 30.4375; to report in weeks divide the number of days by 7; to report in years divide the number of days by 365.25.

Age will be calculated as the number of complete years between a subject's birth date and the date of informed consent. If the birth date is incomplete, the subject's birth year will be used to calculate age.

Idera Pharmaceuticals, Inc.  
Statistical Analysis Plan  
Protocol Number: 2125-MEL-301

---

### **8.2.5 Baseline Definition**

Baseline is defined as the most recent, non-missing value prior to the first study treatment dose date and time. For enrolled subjects who did not receive study treatment during the study, baseline is defined as the latest, non-missing collected value before the date of randomization.

### **8.2.6 Change from Baseline**

Change from baseline will only be calculated for measures that have post-baseline records. Change from baseline for safety measures is calculated as:

- visit value – baseline value.

Percentage change from baseline is calculated as:

- $(\text{change from baseline} / \text{baseline value}) * 100$

If either the baseline or visit value is missing, the change from baseline and percentage change from baseline are set to missing.

### **8.2.7 Treatment Emergence Flag**

A treatment emergence flag will be derived based on the AE start date (and time if available) to determine an AE occurred before or after first dose date of either study drug. If an AE occurred prior to the first dose date, the AE will be designated as not treatment emergent. If an AE occurred after the first dose date, the AE will be designated as treatment emergent. If an AE occurred on the same date or the same date/time of first dose date(time), the AE will be designated as treatment emergent unless 'NOT APPLICABLE' was recorded for the action taken with both study drugs for the combination arm or the AE was considered related to the either study drug. Similar rules will be applied to the ipilimumab alone arm.

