10.1.2. Recording Adverse Events

Procedures for the collection and recording of AEs are as follows:

- AEs are captured from the time of informed consent. Events will be recorded in the AE portion of the electronic data capture (EDC), with particular attention to whether the onset of the event was before or after the administration of the first dose of study drug. All recorded events will be included in applicable line listings, but only events with onset after administration of the first dose will be included in summaries of TEAEs.
- After the Active Follow-up Period, surveillance will be passive (only events brought to the Investigator’s attention will be considered) and only events assessed as SUSARs will be recorded (see [Section 10.1.1.3](#)).
- In accordance with the FDA guidance document – Safety Reporting Requirements for Investigational New Drugs and Bioavailability/Bioequivalence Studies – disease progression does not require reporting as an AE or SAE. However, signs and symptoms related to disease may be reported at the discretion of the Investigator.

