10.1.3.2. Date and Time of Onset

The date and time at which the event was first apparent will be recorded, if known. The time of onset of symptoms may be appreciably earlier than the date and time the Investigator becomes aware of the event. Some events may be apparent to the subject and Investigator independently, and information from each may contribute to the final report. For example, a subject may report the onset of a rash 2 days prior to being seen by a physician who makes a diagnosis of herpes zoster based on appearance and laboratory confirmation. In that case, there is a single AE, with the date of onset based on the date of the initial observation by the subject and a specific description (herpes zoster) based on the clinical exam and tests.

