## 11 SAFETY ANALYSES

All safety analyses will be based on the Safety Set as defined in [Section 6.5](#). Summaries of AEs will include only treatment-emergent AEs (TEAEs), defined as AEs with a start date on or after the date of first dose of study treatment or existing AEs which increase in CTCAE grade after the start of study treatment. If it cannot be determined definitively whether the AE is treatment emergent due to missing or partial onset or end dates, then it will be counted as treatment emergent (see [Section 8.2.7](#) for details).

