Incidence of TEAEs will be summarized by MedDRA PT and time of onset relative to the first exposure of the study drug by 3-week interval during the treatment period. The first onset interval will start at the first dose date and end on the 21st day (Weeks 1-3); the second interval will start on the 22nd day and end on the 42nd day (Weeks 4-6); the third interval will start on the 43rd day and end on the 63rd day (Weeks 7-9); the fourth interval will start of the 64th day and end on the 84th day (Weeks 10-12); the fifth interval will start from the 85th day and end on the 105th day (Weeks 13-15); the sixth interval will start from the 106th day and end on the 126th day (Weeks 16-18); the seventh interval will start from the 127th day and end on the 147th day (Weeks 19-21); and the last will start on the 148th day and end on the 168th day (Weeks 22-24). Adverse events will be assigned to onset categories according to the relative study day when the AE started. AEs with incomplete onset dates will be excluded from this analysis. For subjects who experienced the same AE multiple times and within different onset categories, the event will be counted once in each of the categories in which it started. For each onset category, AE incidences will be calculated by dividing the number of subjects who had each AE during that onset category by the number of subjects who have not dropped out or died at the start of the onset interval. For example, for onset category Weeks 4-6, the denominator will be the number of subjects who have not dropped out or died by the start of Weeks 4-6 interval and were therefore in the risk set for that interval.

Idera Pharmaceuticals, Inc.  
Statistical Analysis Plan  
Protocol Number: 2125-MEL-301

---

All AEs will be listed. This listing will include treatment arm, age, sex, start date and study day, end date and study day, grade, serious (yes or no), irAE (yes or no), relationship to treatment (yes or no), action taken, outcome, and preferred and verbatim terms.

The following summaries will be provided:

- Overall Summary of Treatment-Emergent Adverse Events
- Treatment-Emergent Adverse Events by System Organ Class and Preferred Term
- Treatment-Emergent Adverse Events by Preferred Term
- Treatment-Emergent Adverse Events by Preferred Term and Maximum Grade

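### SAP 8.2.7 as written makes a drug-related adverse event on the first-dose date not treatment emergent, and SAP 11.6 censors subjects who had the event

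*SAP*

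**What the plan says.** **SAP 8.2.7** bases the flag on the event's start date, and on its time where available. Events before the first dose are not treatment emergent and events after it are. For an event that coincides with the first dose, the default is put this way: "of first dose date(time), the AE will be designated as treatment emergent unless". The first exception is an entry of NOT APPLICABLE, and the second is joined to it by *or*: "for the action taken with both study drugs for the combination arm or the AE was considered related to the either study drug". The ipilimumab-alone arm is to follow the same kind of rule.

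**SAP 11** takes TEAEs to be those "defined as AEs with a start date on or after the date of first dose of study treatment", and it adds a second limb for worsening: "or existing AEs which increase in CTCAE grade after the start of study treatment". If the status is unclear "due to missing or partial onset or end dates, then it will be counted as treatment emergent", with a pointer to 8.2.7 for details.

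**SAP 11.2**, on the TEAE table by 3-week interval: "The first onset interval will start at the first dose date".

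**Protocol 10.1.2**: "only events with onset after administration of the first dose will be included in summaries of TEAEs". **Protocol 10.1.3.2**: "The date and time at which the event was first apparent will be recorded, if known".

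Two imputation rules bear on the flag. SAP 8.1.1 sets a missing relationship to related. SAP 8.1.2 moves some partial start dates to the first-dose date (day missing in the first-dose month, or day and month missing in the year of study start) and uses the imputed date for the flag.

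**SAP 11.6**, for the Kaplan-Meier analysis of time to first AESI, censors subjects who completed or terminated the study *with* the event at the time they left. It gives no rule for subjects without it.

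**The concern.** Relatedness to study drug should be a reason to keep a same-day event in the treatment-emergent summaries. As drafted, it is a reason to remove the event.

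The events at risk are same-day reactions to a first infusion or first injection, and the type lost differs by arm. Under Protocol 9.3.3, Arm A starts ipilimumab at Week 1, so related reactions on the day of its first infusion would drop out. Arm B starts with IMO-2125 and first receives ipilimumab at Week 2. It would lose same-day reactions to the first injection but keep those to the first ipilimumab infusion. The TEAE comparison between arms would then be distorted in kind as well as in number.

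The supplementary AESI search in SAP 11.6 starts from TEAEs, so an error in the flag carries into it. Both AESI searches are tied to tilsotolimod injections (the name SAP 11.6 uses for the investigational drug), so the ipilimumab asymmetry does not carry over to AESIs.

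**Working it through.** The plan gives no figure to reproduce here. The check is one of logic, followed by a count of the outputs that use the flag.

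**Step 1. An event on the first-dose date.** Let NA mean that NOT APPLICABLE was recorded for both drugs, and R that the event was considered related to either drug.

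- SAP 8.2.7 as written: emergent = not (NA or R).
- SAP 11: emergent in every case.
- Probable intent: emergent = not (NA and not R).

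| NA | R | 8.2.7 as written | Probable intent | SAP 11 |
|---|---|---|---|---|
| no | no | emergent | emergent | emergent |
| no | yes | **not emergent** | emergent | emergent |
| yes | no | not emergent | not emergent | emergent |
| yes | yes | **not emergent** | emergent | emergent |

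As written, 8.2.7 agrees with SAP 11 in 1 of 4 rows and contradicts it in both related rows. Under the probable intent they agree in 3 of 4; the unrelated, NOT APPLICABLE row still differs.

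**Step 2. Other SAP rules.**

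- Because SAP 8.1.1 sets a missing relationship to related, this worst-case safeguard would, under 8.2.7 as written, remove a first-dose-date event from the summaries.
- Events moved to the first-dose date by SAP 8.1.2 meet the same exception. They are lost only if the SAP 11 default for undetermined status is not applied, and 8.2.7 does not repeat that default.
- 8.2.7 also omits the SAP 11 provision for existing events that worsen in grade.

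**Step 3. Outputs that use the flag (SAP 16.2).**

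- Treatment-emergent tables: 14.3.2.1 to 14.3.2.7.2 (15) + 14.3.3.1 to 14.3.3.8 (8) + 14.3.4 (1) + 14.3.5.1.1 to 14.3.5.5 (6) + 14.3.6.1 to 14.3.6.6 (6) + 14.3.7.1 and 14.3.7.2 (2) = 38.
- Restricted to related events: 14.3.2.3, 14.3.2.4.2, 14.3.2.5.2, 14.3.2.7.1, 14.3.2.7.2 (5) + 14.3.3.5 to 14.3.3.8 (4) + 14.3.5.2 (1) + 14.3.6.2 and 14.3.6.4 (2) = 12.
- Marked IDMC: 10 in the 14.3.2 series + 14.3.3.5 to 14.3.3.8 (4) + 14.3.5.1.1 (1) + 14.3.6.1 and 14.3.6.3 (2) = 17.
- Related-only and marked IDMC: 14.3.2.3, 14.3.2.7.1, 14.3.2.7.2 (3) + 14.3.3.5 to 14.3.3.8 (4) = 7.

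These are counts of exposed outputs, not of events lost.

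**Step 4. SAP 11.6.** As written, a subject with an AESI who has completed or left the study is censored rather than counted. As an illustration, assume 200 subjects, of whom 10, 20 or 40 have an AESI (5%, 10% or 20%) and have since left the study. The analysis then has 0 events in each case, and no quartile can be estimated.

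**The case against.** The strongest reply is that 8.2.7 can be parsed another way, with relatedness as an override: not emergent if NOT APPLICABLE, unless related. That is the probable-intent column above. The grammar does not favour it, and it supports the proposed rewording. A flag rule that can be read to opposite results for related events needs correcting on either reading.

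Several narrower points stand:

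- **Timed onsets.** 8.2.7 uses time where available, so an event timed after the dose may fall in its *after* branch. The text does not settle this. The claim is therefore limited to related first-dose-date events, at least those without a recorded time after the dose.
- **Supporting conflicts.** Protocol 10.1.2 can be read as a necessary condition only, and SAP 11.2 bins events already flagged as TEAEs. Both are weaker support; the conflict with SAP 11 stands without them.
- **Programming.** SAP 8.2 refers to dataset specifications that are not available here. They may code the flag correctly, but they do not correct the SAP.
- **Mitigation.** SAP 7 and 11.2 say that all data and all AEs are listed. The SAE listing covers all SAEs with an emergence flag and goes to the IDMC. The initial AESI search by LLT is not stated to be limited to TEAEs.

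The SAP 11.6 wording is an unrelated one-word slip with obvious intent, and it adds no weight to the 8.2.7 point.

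**Conclusion.** The concern holds. Followed as written, SAP 8.2.7 gives the wrong answer for drug-related events on the first-dose date and contradicts SAP 11 in both related cases. SAP 11.6 as written censors subjects it should count. Both are most likely drafting errors, but they are stated rules that yield a wrong safety result if programmed literally.

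The size in events is unknown. It depends on how many related events fall on the first-dose date without a recorded later time, and on how the dataset specifications code the flag. The effect is confined to safety summaries: ORR, OS, alpha and sample size are not involved. AESI incidence (14.3.7.1) and the AESI listing do not use the 11.6 censoring rule. This should be fixed before the tables are run.

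**What to change.** Have the sponsor confirm the intent, then make these edits.

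1. **SAP 8.2.7.** Where recorded times settle the order, an event starting after the first dose is treatment emergent and one starting before it is not. Otherwise, an event with a complete start date equal to the first-dose date is treatment emergent, unless action taken is NOT APPLICABLE for all study drugs **and** the event is not related to any study drug.
2. **SAP 8.2.7, imputed dates.** State that events whose start date was imputed to the first-dose date stay treatment emergent where the SAP 11 default for undetermined status applies.
3. **SAP 8.2.7, worsening.** Repeat the SAP 11 provision for existing events that increase in CTCAE grade.
4. **SAP 11.** Make the same-date wording match item 1. The alternative is to drop the exception from 8.2.7 so that SAP 11 stands unchanged. Either removes the one remaining disagreement.
5. **SAP 11.6.** Change *with* to *without* for the event in the censoring sentence.

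The cost is a few sentences in 8.2.7, a clause in SAP 11, one word in 11.6, and a check that the dataset derivation matches. Protocol 10.1.2 can stay as it is, and no new data are needed.

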### **8.2.8 Multiple Assessments**

#### **8.2.8.1 Disease Assessment Scans**

When a subject has disease assessment imaging for a single visit on multiple dates, the date of the disease assessment will be assigned using the following rules: For RECIST v1.1 response, if the visit response is Progressive Disease (PD), the date of progression is the earliest of:

- all dates of target lesion scans when the target lesion response is PD

Idera Pharmaceuticals, Inc.  
Statistical Analysis Plan  
Protocol Number: 2125-MEL-301

---

- all dates of non-target lesion scans at which the non-target lesion status is unequivocal progression
- all scan dates documenting new lesion(s)

For both sets of response criteria, if more than one source of PD is reported, then the date assigned is the earliest across all sources of PD. If none of the above dates is available, the date of the earliest scan (if available) or visit date for the assessment at which PD is reported is assigned. If the visit response is PD by symptomatic deterioration, the date is the date of the disease assessment visit.

If the visit response is Stable Disease (SD), the date of SD is the earliest date of any lesion assessment at the visit.

If the visit response is Complete Response (CR) or Partial Response (PR), the date of CR or PR is the latest date of any lesion assessment at the visit. If all assessment dates are missing or not reported, then a date of response cannot be assigned.

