The appearance of any new unequivocal malignant lesion indicates PD. If a new lesion is equivocal, for example due to its small size, continued assessment will clarify the etiology. If repeat assessments confirm the lesion, then progression should be recorded on the date of the initial assessment. A lesion identified in an area not previously scanned will be considered a new lesion.

4. Supplemental Investigations

- If CR determination depends on a residual lesion that decreased in size but did not disappear completely, it is recommended the residual lesion be investigated with biopsy or fine needle aspirate. If no disease is identified, objective status is CR.
- If progression determination depends on a lesion with an increase possibly due to necrosis, the lesion may be investigated with biopsy or fine needle aspirate to clarify status.

5. Attentive Progression

Patients requiring discontinuation of treatment without objective evidence of disease progression should not be reported as PD on tumor assessment CRFs. This should be indicated on the end of treatment CRF as off treatment due to Global Deterioration of Health Status. Every effort should be made to document objective progression even after discontinuation of treatment.

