### **10.2.6 Duration of Response**

DoR will be derived separately for the assessments by blinded independent reviewer and the investigator. DoR will be derived using RECIST v1.1, defined as the time in months between the date of the first instance of confirmed CR or PR as the best overall response to the day before the first date that recurrent or progressive disease is objectively documented or date of death. For subjects who have attained CR or PR as the best overall response but do not have progressive disease or died, they will be censored at the same time they will be censored for the primary definition of PFS (See [Appendix Section 16.4](#)). Subjects who do not respond will not be included in this analysis.

DoR will be described using Kaplan-Meier estimates with 95% CIs. If there are sufficient number of events, median, first and third quartiles, minimum and maximum for DoR with corresponding 95% CIs will be reported. CIs will be estimated using the Brookmeyer-Crowley method [[Brookmeyer, 1982](#)] with log-log transformation. Summaries will also include the number of subjects at risk, the number of subjects with events, and the number of subjects censored.

The following summaries and figures for DoR will be provided:

- DoR based on Independent Reviewer-Assessed ORR by RECIST v1.1 for ORR Responder
- DoR based on Investigator-Assessed ORR by RECIST v1.1 for ORR Responder
- Kaplan-Meier Plot of DoR based on Independent Reviewer-Assessed ORR by RECIST v1.1 for ORR Responder
- Kaplan-Meier Plot of DoR based on Investigator-Assessed ORR by RECIST v1.1 for ORR Responder

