### **10.2.8 Analysis of Progression-Free Survival**

PFS is defined as the time in months from the date of randomization to progression by RECIST v1.1 or death from any cause. The date of disease progression will be the date of the scan for the first objectively documented PD per RECIST v1.1. Subjects who do not progress including those who have started new anticancer therapy, withdrawn from the study, or been lost to follow-up without disease progression will have their PFS time censored at the last valid disease assessment, defined as a scheduled or unscheduled visit with a disease assessment of CR, PR, or SD (for RECIST v1.1). More detailed censoring rules are in [Appendix Section 16.4](#).

PFS assessed by investigator and independent reviewer will be analyzed using Kaplan-Meier method, the median, first and third quartiles with corresponding 95% CIs are calculated by the Brookmeyer-Crowley method with log-log transformation. If there are a sufficient number of events, Kaplan-Meier estimates and 95% CIs will also be produced at PFS landmark time points at 6 months, 1 and 2 years. The 95% CIs for Kaplan-Meier estimates at each of the PFS landmark time points will be calculated using Greenwood's formula with log-log transformation. Summaries will also include the number at risk, the number of subjects with events, and the number of subjects censored along with their corresponding reason for censoring. Figures will use the Kaplan-Meier estimates and identify the number of subjects at risk at each scheduled visit and censored times on the curve.

The following summaries and figures will be provided for PFS:

- Summary of Independent Reviewer-Assessed PFS by RECIST v1.1
- Summary of Investigator-Assessed PFS by RECIST v1.1
- Kaplan-Meier Plot of Independent Reviewer-Assessed PFS by RECIST v1.1
- Kaplan-Meier Plot of Investigator-Assessed PFS by RECIST v1.1

The following efficacy listing will be provided:

- Progression-free Survival by Independent Reviewer-Assessed and Investigator-Assessed RECIST v1.1

Idera Pharmaceuticals, Inc.  
Statistical Analysis Plan  
Protocol Number: 2125-MEL-301

---

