## 16.4 CENSORING RULE FOR PFS

The following censoring rules will be used for PFS analysis to be consistent with FDA guidance on Clinical Trial Endpoints for the Approval of Cancer Drugs and Biologics.

[source: <https://www.fda.gov/downloads/Drugs/Guidances/ucm071590.pdf>]

Situation	Date of Progression or Censoring	Outcome
No baseline tumor assessments	Randomization	Censored
Progression documented between scheduled visits	Earliest of: 
 
• Dates of target lesion scans when the target lesion response is PD;
 
or
 
• Dates of non-target scans at which the non-target lesion status is unequivocal progression;
 
or
 
• Dates of scans documenting new lesion (if progression is based on new lesion)
 
	Event
No progression	Date of the last valid disease assessment, defined as a scheduled or unscheduled visit with a disease assessment of CR, PR, or SD	Censored
Treatment discontinuation for undocumented progression	Date of the last valid disease assessment, defined as a scheduled or unscheduled visit with a disease assessment of CR, PR, or SD	Censored
Treatment discontinuation for other reasons	Date of the last valid disease assessment, defined as a scheduled or unscheduled visit with a disease assessment of CR, PR, or SD	Censored
New anticancer treatment started	Date of the last valid disease assessment, defined as a scheduled or unscheduled visit with a disease assessment of CR, PR, or SD, prior to new anticancer treatment started	Censored
Death without documented progression and is not after two or more missed visits	Date of death	Event
Death or progression after two or more missed visits	Date of the last valid disease assessment, defined as a scheduled or unscheduled visit with a disease assessment of CR, PR, or SD	Censored

Idera Pharmaceuticals, Inc.  
Statistical Analysis Plan  
Protocol Number: 2125-MEL-301

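### SAP 8.2.8.1 dates progression by symptomatic deterioration, which protocol 20.2 bars and the SAP's PFS and DoR sections do not count, and nothing says which rule prevails

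*SAP*

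**What the plan says.** SAP 8.2.8.1 sets the date of a disease assessment when one visit spans several imaging dates. The rules for PD open with "For RECIST v1.1 response, if the visit response is Progressive Disease (PD), the date of progression is the earliest of" and then list three sources: target lesion scans, non-target scans and scans showing new lesions. A fallback follows: "If none of the above dates is available, the date of the earliest scan (if available) or visit date for the assessment". The paragraph closes with "If the visit response is PD by symptomatic deterioration, the date is the date of the disease assessment visit".

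Protocol 20.2 excludes that last category from tumour assessment records: "Patients requiring discontinuation of treatment without objective evidence of disease progression should not be reported as PD on tumor assessment CRFs". Such a case goes elsewhere: "This should be indicated on the end of treatment CRF as off treatment due to Global Deterioration of Health Status".

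The SAP's endpoint sections follow the protocol. For PFS, SAP 10.2.8 says "The date of disease progression will be the date of the scan for the first objectively documented PD per RECIST v1.1". For DoR, SAP 10.2.6 runs to "the first date that recurrent or progressive disease is objectively documented or date of death" and borrows the PFS censoring. SAP 16.4 has a row headed "Treatment discontinuation for undocumented progression", which censors at the last assessment of CR, PR or SD.

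The response-rate sections are less specific. SAP 10.1.1 (ORR) and SAP 10.2.5 (DCR) require the response, or stable disease, to come before PD and before new anticancer therapy. Neither limits PD to objectively documented PD.

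**The concern.** The SAP recognises and dates a PD category that the protocol says should not be recorded as PD, and that the SAP's own PFS and DoR definitions do not count. It states no order of precedence. SAP 5 says that no planned analysis differs from the protocol, so this is not a declared departure.

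The case is foreseeable. Protocol 8.3.1 lists clinical progression among the reasons for stopping study drug, and the SAP authors provided a date for it. The trial is open-label, so an investigator who judges that a subject has deteriorated knows the arm. If those judgements were counted as RECIST v1.1 progression, investigator PFS and response rates would mix measured tumour change with unblinded opinion.

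**Working it through.** The plan states no figure on this point, so the check is mainly a reading of the rules side by side. Take one subject who declines clinically at Week 12, with no scan evidence of progression, and whose investigator nevertheless records a visit response of PD.

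| Rule | Treatment of this subject |
|---|---|
| Protocol 20.2 | Not reported as PD; recorded on the end-of-treatment form |
| SAP 8.2.8.1 | PD, dated at the Week 12 visit |
| SAP 10.2.8 (PFS) | No event, because no objectively documented PD |
| SAP 16.4 | Censored at the last CR, PR or SD assessment |
| SAP 10.2.6 (DoR, if a responder) | No event; censored as for PFS |
| SAP 10.1.1 and 10.2.5 (ORR, DCR) | Open: any PD may cut off a later response or stable disease |

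Three things follow.

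1. If sites follow protocol 20.2, the record never arises and the SAP sentence has no effect.
2. If it does arise, the PFS and DoR sections exclude it. It becomes an event there only if a programmer lets the dating rule override them.
3. For response rates, no wording excludes it. Treatment after progression is allowed at the investigator's discretion (protocol 9.3.3.2), and protocol 20.3 describes pseudoprogression, so an objective response after a symptomatic PD is possible and could be disqualified.

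Deleting the sentence alone would not settle the matter. The visit would still carry a PD category, and the fallback would still date it.

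**Size for PFS.** The documents give no rate of symptomatic PD, so this is an illustration.

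- Arm size: 454 / 2 = 227 (protocol 15.1, 1:1 randomization).
- Assumed share with symptomatic PD at Week 12: 5%, so 0.05 × 227 = 11.35, taken as 11 subjects.
- Week 12 is the first scheduled assessment after baseline (protocol 11.1). Under SAP 16.4 these 11 have no earlier post-baseline CR, PR or SD, so they leave the risk set before Week 12.
- Let p be Week 12 PFS among the other 216, with no other early censoring.

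Censored earlier: PFS(12) = p.

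Counted as events: PFS(12) = p × 216/227.

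Shift = p × 11/227 = 0.048p, or 4.8 points times p.

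- p = 0.4: 0.4 × 4.8 = 1.9 points
- p = 0.7: 0.7 × 4.8 = 3.4 points

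The values 0.4 and 0.7 are assumptions. The ceiling is 4.8 points, at p = 1. No corresponding figure can be given for ORR or DCR.

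**The case against.** The best defence is that SAP 8.2.8.1 assigns dates and does not define events. Events are defined in SAP 10.2.6, 10.2.8 and 16.4, which already require objective evidence, and protocol 20.2 stops the record at the site. This largely stands for PFS and DoR. It does not remove the ambiguity, because precedence is unstated and the response-rate sections carry no such qualifier.

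The offending sentence also follows a reference to both sets of response criteria, so it may partly serve the irRECIST listings. The text does not settle this, and the rules are introduced as RECIST v1.1 rules.

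The unqualified condition on PD sits in the blinded-review ORR section. SAP 10.2.1 (investigator ORR) and SAP 10.2.4 (durable response rate, DRR) do not repeat it. It may carry over to them. SAP 10.2.5 does use it, and applies a similar summary to investigator-assessed DCR.

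A reader might infer that blinded review could never reproduce a symptomatic PD, so that the concordance tables would show disagreement created by this rule. The documents do not support that. Protocol 8.1.1 gives central reviewers clinical as well as imaging results. The tables in SAP 10.2.2 compare response categories, which depend on what each reader recorded and not on the date that 8.2.8.1 assigns.

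**Conclusion.** The conflict is real and the text does not resolve it. A subjective PD could enter the investigator-assessed endpoints: through misapplied precedence for PFS and DoR, and through an unqualified condition for best overall response, ORR and DCR.

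A reader might go further and say that such progressions will enter these endpoints. That would require sites to depart from protocol 20.2 and, for PFS and DoR, the dating rule to displace the endpoint sections. A reader might also expect a full 5-point shift, or a 5-point difference between arms if 10% of one arm and 5% of the other were affected. Those rates are not in the documents, and the 5-point shift leaves out the multiplication by p. On the assumptions above, the shift for 5% of an arm is about 2 to 3.4 points.

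Severity is low. OS does not use progression, and primary ORR is read by blinded independent review. SAP 7.2 makes all secondary analyses descriptive. No alpha, power or sample-size figure depends on this rule.

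**What to change.** Before database lock:

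1. Delete the symptomatic-deterioration sentence from SAP 8.2.8.1.
2. State that symptomatic deterioration alone, without target progression, unequivocal non-target progression or a new lesion, is not a RECIST v1.1 PD for best overall response, ORR, DCR, DRR, DoR or PFS, and is handled under the undocumented-progression row of SAP 16.4.
3. Keep the fallback date in SAP 8.2.8.1, but reserve it for PDs reported on objective grounds whose lesion dates are missing. Setting every PD without a lesion source to not evaluable would go too far, because it could erase real progressions with incomplete lesion data.
4. Optionally, add a labelled supportive investigator PFS that counts clinical progression as an event.

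The cost is one deleted sentence, one added statement and one derivation rule. There may be slightly fewer investigator PFS events. The change applies the sponsor's own rules in protocol 20.2 and SAP 16.4, and leaves clinical management untouched.
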